3.10 Data analysis

3.10.1 Case record form (CRF)

CRF consisted of standardized forms to collect data regarding enrollment form, demographic data, follow-up data, polysomnographic data, CPAP adherence data, fetal ultrasound data and pregnancy outcomes. Pregnancy and fetal outcome will be extracted from the clinical record after delivery into specific CRF.

3.10.2 Database

CRF consisted of eligibility form, enrollment form for baseline demographic data, follow-up visit form, PSG form, CPAP adherence form, ultrasound form, delivery form, and neonatal form. Data will be extracted from the CRF into the database. Database will be built with Epidata software to ensure the organization and cross-checking of the data. Data storage will be kept in the computer and hard-disc for back-up at 2 sites (Ramathibodi Sleep Disorder Center and Section of Clinical Epidemiology and Biostatistics: CEB). Additional back-ups of data will be kept in the CEB's server.

3.10.3 Data quality control

Data from each site will be extracted and double entry into the database to ensure correctness of the data within 1 week after data acquisition. Cross-checking and logical check will be done every month by a statistician.

3.10.4 Statistical analysis

- Baseline demographic and clinical variables will be summarized using mean and its standard deviation (SD) or median and inter-quartile range as appropriate for continuous data, whereas categorical variables are summarized in frequencies and percentage. Comparisons of baseline characteristics between the 2 groups will be performed using t-test for the continuous variables and χ^2 test for the categorical variables.

- A blinded evaluation is planned to assess the observed primary end point by a clinical outcome assessment committee.
- The null hypothesis of the primary outcome for the Δ change of blood pressure (DBP) between treatment and controls are tested at 2-sided significant level of p -value <0.05 using t -test.
- Analyses for repeated measurement of secondary outcomes for continuous variables such as 24-hour blood monitoring, glucose level, Uterine artery Doppler ultrasound pulsatile index, estimated fetal growth, at 6-8 weeks after randomization, and during 2-3rd trimesters compared to baseline are performed using a longitudinal data analyses with linear mixed model.
- Analyses of secondary outcome of categorical data such as composite outcome 1 to 3, and individual outcome, control of BP, or non-dipping BP pattern will be compared between CPAP and control groups using χ^2 test, or Fisher exact test as appropriate.
- Gestational diabetes, as one of the inclusion criteria, was not included in endpoint analyses as initially planned.
- Predictors for composite outcome, and individual outcomes will be analyzed with multivariate logistic regression model adjusting for other co-variates.
- Statistical analyses will be performed according to the intention-to-treat analysis. Per-protocol analysis will then be analyzed for the comparisons of the results.

- In addition, per-protocol (PPA) and as-treated analyses (ATA) with counterfactual approach were also applied to deal with protocol violation using instrumental variable regression.
- We did not apply imputation for missing data because they were not used for the analysis.
- All statistical analyses are considered significant at the threshold level of 2-sided p-value < 0.05. Statistical analyses are performed using STATA Version 13.1 (StataCorp, College Station, TX).
- Interim analysis was not performed as initially planned, due to lower than expected number of deliveries when 50% of enrollments were achieved. Decisions were reported to the Ethic committee for approval.

[51-53].

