1.3 Research Objectives

1.3.1 **Primary Objective:** To compare whether the treatment effect of CPAP on SDB during pregnancy can improve blood pressure control in high risk pregnancy

- Systolic/diastolic blood pressure during daytime ANC at 10:00-12:00 am at randomization (GA 0-16 week), 1.5-2 month after randomization (GA 18-20 week), and 3-4 month after randomization (GA 24-28 week), 5-6 month after randomization (GA 32-34 week) and monthly (GA>35 week) until delivery

1.3.2 **Secondary Objective:**

- To compare the composite outcome of pre-eclampsia/GHT, GDM, fetal growth restriction, and pre-term labor between the CPAP treatment and control groups. And individual outcomes.
- To compare the night-time blood pressure compared to control group. 2nd outcome

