3.7.2 Control Group

- Subjects will receive standard antenatal care and follow-up plan similar to the intervention group.

Primary outcome

- Systolic and diastolic blood pressure, which will be measured at rest using sphygmomanometer twice on both arms by research nurses during daytime ANC at 10:00-12:00 pm at randomization (GA 0-16 week), 1.5-2 month after randomization (GA 18-20 week), and 3-4 month after randomization (GA 24-28 week), 5-6 month after randomization (GA 32-34 week) and monthly (GA>35 week) until delivery

Secondary outcome

- 24-hour ambulatory blood pressure monitoring (daytime versus night time) using the non-invasive technique from pulse transit time (SomnoTouch NIBP).
- Pregnancy complication listed as composite endpoints below

(Composite endpoint): A combination of clinical endpoints in maternal and fetal outcomes, data from Ramathibodi hospital during 2013-2014) *

- **Composite 1:** hypertensive disorder of pregnancy;
- **Composite 2:** hypertensive disorder of pregnancy or preterm labor or fetal growth restriction
- **Composite 3:** Preterm labor or fetal growth restriction, or severe pre-eclampsia or eclampsia or death; (composite 3 incidence=10%)

*Given that the incidence of hypertensive disorder incidence= $136/3787=3.6\%$;
gestational diabetes incidence= $601/3787=15.9\%$; fetal growth restriction incidence= $157/3787=4.1\%$; preterm labor incidence=10%; and severe pre-eclampsia/eclampsia/HELLP syndrome incidence= $(43+ 1+3=46/3787=1.2\%)$, respectively.

- Individual component of the composite endpoints including incidence of hypertensive disorder of pregnancy, gestational diabetes, preterm labor, and fetal growth restriction
- Glucose level, Oral Glucose Tolerance Test (OGTT), HbA1C
- Fetal ultrasound results: uterine Doppler arterial blood flow, fetal growth restriction
- Neonatal outcome: birth-weight, APGAR score, Length of stay, NICU admission

- Placenta character: weight will be measured at birth by the neonatal nurse.

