3.9 Sample size estimation

3.9.1 Based on primary outcome

Power	Alpha	SD	Mean difference	M (Intervention /control)	Intervention N	Control N	Total N
0.80	0.05	7.4	2.0	1	216	216	432
0.80	0.05	7.4	2.5	1	139	139	278
0.80	0.05	7.4	3.0	1	111	111	222
0.80	0.05	7.4	3.5	1	71	71	142

Sample size calculation will be based on the primary outcome, which is the reduction in blood pressure. Based on the previous data by Reid, et al the mean diastolic blood pressure during pregnancy approximates 92.7 ± 7.4 mmHg [50]. Type I & II error and a ratio of intervention versus control are set at 0.05, 0.2, and 1:1, respectively. Estimated sample sizes are display below according to level of mean differences.

A systematic review and meta-analysis showed that CPAP could reduce blood pressure in OSA patients of -2.87 (95%CI -5.18-0.55) [25]. We, therefore, set mean difference of at least 2.5 mmHg, which will require 278 subjects to enroll. Taking into account for loss to follow-up of 20%, a total of 334 subjects are required (167 each arms). Additional number of subjects to be recruited was increased during January 2019-May 2019 up to 360 cases to allow for the potential subject discontinuation of the study with approval of the ethic committee.

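### The primary outcome is SBP and DBP at several visits, but the only primary test is a t-test on DBP change that names no visit, leaves SBP's status unstated and gives up precision from baseline DBP

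*Protocol*

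**What the plan says.** Section 1.3 of the Protocol sets the primary objective on "Systolic/diastolic blood pressure during daytime ANC at 10:00-12:00 am at randomization (GA 0-16 week") and at later visits. The primary outcome, listed under section 3.7.2, is "Systolic and diastolic blood pressure, which will be measured at rest using sphygmomanometer twice on both arms by research nurses". After randomization the readings fall at GA 18-20 and 24-28 weeks, then "5-6 month after randomization (GA 32-34 week) and monthly (GA>35 week) until delivery". The Combined protocol and SAP gives the same variables and visits.

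Section 3.10.4 of both documents states one null hypothesis for the primary outcome. It concerns the "change of blood pressure (DBP) between treatment and controls are tested at 2-sided significant level of" 0.05, by t-test. It names no visit, no average over visits, no covariate and no stratification factor, and it does not mention SBP. For repeated continuous secondary outcomes the same section does give time points, and says the analyses "are performed using a longitudinal data analyses with linear mixed model". Blood pressure appears once more, as a secondary categorical outcome: "control of BP, or non-dipping BP pattern will be compared between CPAP and control groups" by chi-squared or Fisher test.

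On sample size, section 3.9.1 says "Sample size calculation will be based on the primary outcome, which is the reduction in blood pressure", and then uses a mean DBP of 92.7 with SD 7.4 mmHg. Section 3.3 of the Protocol stratifies randomization by trimester; section 3.3 of the Combined protocol and SAP stratifies by centre.

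**The concern.** There are two gaps. The first is identification. At least four post-randomization occasions are scheduled, and a change in DBP can be computed at any of them. Without a named visit or average, a reader cannot tell which DBP result is the primary one or whether it was fixed before the data were seen. The Protocol Flow Chart does not settle this: it has two post-enrolment DBP columns (2nd and 3rd trimester), against three fixed follow-ups plus monthly readings in the outcome definition. The choice also affects who is analysed, because the Protocol applies no imputation and a woman who delivers before a late visit has no reading there. SBP is labelled primary, yet nothing says whether its result is confirmatory or descriptive.

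The second gap is precision. Baseline DBP is collected on everyone and a mixed model is already planned for secondary outcomes, but the primary comparison uses a raw change score. That can cost power which is available at no extra burden.

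**Working it through.** **Inputs.** From section 3.9.1: difference 2.5 mmHg, SD 7.4, power 0.80, 1:1 allocation, 139 per arm before loss, 167 per arm after the stated allowance, and a later increase to 360 in total (180 per arm; 180 × 0.8 = 144 per arm after 20% loss). From section 3.10.4: two-sided 0.05. Assumed: the baseline-to-visit correlation rho, taken over 0.3 to 0.7, and SD 7.4 at both times.

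**The plan's own figure.** Normal approximation: n = 2 × (1.960 + 0.842)² × 7.4² / 2.5² = 2 × 7.849 × 54.76 / 6.25 = 137.5, so 138 per arm. The noncentral-t calculation gives 139 per arm (278 in total), as stated. The figure reproduces, for DBP only.

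**Which SD it uses.** The 7.4 comes with a mean of 92.7, so it is the SD of a DBP level. The planned test is on a change:
- SD of change = 7.4 × √(2(1 − rho))
- SD after regression on baseline = 7.4 × √(1 − rho²)
- variance ratio, adjusted to change = (1 − rho²) / (2(1 − rho)) = (1 + rho)/2

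If the SD is 7.4 at both times, the SD of change is also 7.4 when rho = 0.5. Other combinations give the same value: SD 8.0 at both times with rho 0.57 gives 8.0 × √0.86 = 7.4. So 7.4 is not shown to be wrong for the change score; the documents leave it unverified.

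**Power for 2.5 mmHg (noncentral t), change score vs baseline-adjusted**

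| rho (assumed) | SD | variance ratio | 139/arm | 144/arm | 180/arm | n/arm for 80% |
|---|---|---|---|---|---|---|
| 0.3 | 8.76 vs 7.06 | 0.65 | 0.66 vs 0.84 | 0.68 vs 0.85 | 0.77 vs 0.92 | 194 vs 127 |
| 0.5 | 7.40 vs 6.41 | 0.75 | 0.80 vs 0.90 | 0.82 vs 0.91 | 0.89 vs 0.96 | 139 vs 105 |
| 0.7 | 5.73 vs 5.28 | 0.85 | 0.95 vs 0.98 | 0.96 vs 0.98 | 0.98 vs 0.99 | 84 vs 72 |

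**When the change score reaches 80%.** The largest SD of change giving 80% power is 7.41, 7.55, 8.13 and 8.44 at 139, 144, 167 and 180 per arm. With rho = 1 − SD_change² / (2 × 7.4²), the thresholds are about 0.50, 0.48, 0.40 and 0.35.

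**Illustration only: picking the visit by its result.** If the best of the three fixed follow-ups were taken at 0.05 each, type I error would be 0.125, 0.118 or 0.109 at an assumed between-visit correlation of 0.5, 0.6 or 0.7. This leaves out the monthly readings, and the documents describe no such selection.

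**The case against.** The case for the plan is substantial. A two-sample t-test on change is a valid test. It does not ignore baseline DBP: it subtracts it, which amounts to regression with the coefficient fixed at 1. At rho 0.5 it has the intended 0.80 power with 139 per arm, and at 180 per arm 0.89. The variable is not really in doubt either: the single null hypothesis has DBP in brackets, and the sample size rests on DBP alone. Nor is any effect of the stratification factor on DBP change shown. Entry is at under 16 weeks, so stratifying by trimester may matter little.

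All of that stands, and it rules out several stronger readings that a reader might infer:
- That the trial is underpowered. This would need a rho below about 0.5 at 139 per arm (SD 7.4 at both times), and no section gives rho.
- That type I error is inflated to 11-13%. That needs the visit to be chosen by its result, which the documents nowhere say.
- That SBP and DBP are co-primary tests with no multiplicity control. Only one hypothesis is stated; what is missing is a sentence on what the SBP result counts for.

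These points do not supply a visit, and they do not recover the precision lost by fixing the coefficient at 1.

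**Conclusion.** The point holds as a recommendation, not as a fatal flaw. The primary test names no visit or average, and SBP is called primary without a hypothesis or a stated status; these are missing details that a short text can supply. The analytic point is precision. With equal SDs, regression on baseline DBP has (1 + rho)/2 of the variance of the change score, which at 139 per arm raises power from 0.80 to 0.90 at rho 0.5. Over rho 0.3 to 0.7 the gain runs from 0.18 (0.84 − 0.66) down to 0.03 (0.98 − 0.95). These figures rest on an assumed rho, SD 7.4 at both times and a 2.5 mmHg difference. They show available precision left unused; they do not prove a shortfall.

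**What to change.** The route depends on whether DBP by arm has been seen. The documents do not say. The past tense in section 3.10.4 (for example "Interim analysis was not performed as initially planned") and the analysis dates of November 2019 to July 2020 in section 3.12 make it likely.

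**If DBP by arm has not been seen:**
1. Name one primary DBP contrast, either a single visit or an average over visits. Make SBP and the other visits secondary.
2. Estimate it by ANCOVA or a linear mixed model with baseline DBP and the stratification factor actually used (trimester in the Protocol, centre in the Combined protocol and SAP).
3. State the missing-at-random assumption and how women who deliver before the visit are handled.
4. Keep the change-score t-test as a sensitivity analysis.

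**If DBP by arm has been seen:**
1. Keep the t-test as primary. State which visit it uses and when that visit was chosen.
2. Show DBP change by arm at every scheduled visit.
3. State the status of SBP.
4. Report the baseline-adjusted model, labelled as supportive.

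The cost is a dated text change on the first route, or one disclosure, one table and one extra model on the second. Neither needs new data or patients. Moving the adjusted model to primary after the data are seen would be post hoc, so the second route does not ask for it.

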1.1.3 Treatment & goal of treatments

Nasal continuous positive airway pressure (CPAP), the standard treatment for OSA in non-pregnant population. CPAP has been shown to reduce cardiovascular mortality, morbidity, and blood pressure [22-25]. However, there are limited data regarding the efficacy of CPAP treatment in pregnancy. CPAP also has been proposed as the adjunct therapy for pre-eclampsia [26]. Despite the safety use of CPAP in pregnant women, the results regarding improvement of pregnancy outcome were lacking [27]. Extrapolation of treatment effect of CPAP from other population may not apply to pregnancy given a different physiology during pregnancy and the effect on the fetus.

We performed a systematic review in search of the existing studies concerning the efficacy of CPAP treatment for SDB during pregnancy. Of the 7 studies included (n=111), only 3 studies were randomized controlled trials (RCT), and the other 4 studies were experimental studies with pre-post design. And of the 3 RCTs, only 1 study initiated CPAP during 1st trimester and throughout pregnancy, the other 2 RCTs applied CPAP for only 1 night.

Significant results for CPAP efficacy regarding BP-lowering effects were reported in 2 studies with the early pregnancy and long-term use, and 2 studies with 1-night use of CPAP in the pre-eclamptic women during 3rd trimester, while 1 study in gestational hypertension women with 1-night use of CPAP showed no treatment effect.

Data on pregnancy outcomes were reported in the 3 long-term early CPAP use studies. While CPAP use seemed to prevent the incidence of preeclampsia, and preterm in pregnant women with chronic HT, this was not the case in women with preeclampsia risk and obesity.

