Based on the rarity of evidence, it is too early to make any conclusion given the limitation in the sample size of the studies, the difference in study design, outcome measurement, the timing and duration of CPAP administration, and characters of subjects included. However, there are some important conclusions that we can make. First, despite the association of SDB and poor maternal and fetal outcomes shown in meta-analyses, there is not enough evidence from existing studies that CPAP treatment can improve pregnancy outcomes particularly, the reduction of preeclampsia and preterm labor. Second, there is no definite cut-off threshold for SDB diagnosis during pregnancy. Third, early and long-term CPAP treatment initiating during 1st trimester seemed more promising than in late pregnancy in improvement of pregnancy outcome. And lastly, in pre-eclamptic women during late pregnancy there is no evidence that CPAP can modify the disease progression, although 1-night CPAP might lower nocturnal blood pressure.

Hence, SDB pose a significant threat to pregnancy and fetus, diagnosis and treatment of SDB during pregnancy are still challenging given the dynamic changes of pregnancy and SDB. Because of the lack of evidence for the diagnostic and treatment threshold for SDB during pregnancy, there is currently no standard guideline to systematically screen and treat for SDB during pregnancy. The situation of SDB during pregnancy is in state of “clinical equipoise”, where the scientific community needs a strong evidence to make any treatment recommendation for the care of pregnant women at risk. It is an urgent need to conduct a randomized controlled trial that can demonstrate the efficacy of CPAP treatment in high risk pregnant women.

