3.2.1 Inclusion criteria (ALL criteria)

- Singleton pregnant women age ≥ 18 years without significant medical conditions such as immunocompromised status, chronic infection (HIV infection, tuberculosis), chronic lung and cardiac conditions, chronic kidney disease, thyroid disease, or neuromuscular disease.
- Pregnant women attending the 1st antenatal care and intending to deliver at one of the study hospitals with gestational age < 16 weeks
- Thai nationality with ability to use Thai language proficiently both in spoken and written language.
- Have been diagnosed as high-risk pregnancy by obstetricians by having any of the following conditions

- a. Chronic hypertension prior to pregnancy
- b. Hypertension during pregnancy before 20week gestation.
- c. Pre-eclampsia/gestational hypertension during recent pregnancy
- d. Obesity defined by pre-pregnancy body mass index (BMI) ≥ 27.5 kg/m²
- e. Having diabetes mellitus or history of gestational diabetes in previous pregnancy
- Having SDB by either definition
 - a) RDI ≥ 5 events/hour by sleep testing at either point of testing during early pregnancy (0-16 GA week) or late pregnancy (GA 24-28 week)
 - b) OR Presence of snoring (either as frequent snoring ≥ 3 times/week or loud snoring) prior to or occurring during pregnancy
- Sign written informed consent

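### Hypertension at entry is recorded and likely to be strongly prognostic, but no stated comparison of CPAP with control adjusts for it, and the composites first need a rule for women who enter with chronic hypertension

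*Protocol*

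**What the plan says.** - **Entry.** Protocol section 3.2.1 admits women on this basis: "Have been diagnosed as high-risk pregnancy by obstetricians by having any of the following conditions". Five conditions follow. Criterion (a) is "Chronic hypertension prior to pregnancy", (b) is hypertension in this pregnancy before 20 weeks, and (d) is obesity. A woman may meet several.
- **Randomization.** Section 3.3 stratifies by trimester in the Protocol and by centre in the Combined protocol and SAP. Neither uses risk condition.
- **Data collected.** Section 3.6.1.1 records underlying disease and blood pressure at the first antenatal visits.
- **Analysis.** Protocol section 3.10.4 tests the change in DBP by t-test. For categorical outcomes, "composite outcome 1 to 3, and individual outcome, control of BP, or non-dipping BP pattern will be compared between CPAP and control groups", by chi-square or Fisher exact test. A later bullet plans a multivariable logistic regression for predictors of the composite and individual outcomes. It does not name the covariates or say that treatment is the term of interest. Neither document plans an analysis by risk condition.
- **Background.** Section 1.1.3 reports: "While CPAP use seemed to prevent the incidence of preeclampsia, and preterm in pregnant women with chronic HT", and then "this was not the case in women with preeclampsia risk and obesity". The same discussion adds that "it is too early to make any conclusion given the limitation in the sample size of the studies".

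**The concern.** The five routes of entry bring together women whose later risk of hypertensive disorder, and whose course of blood pressure, can be expected to differ. When a strong baseline predictor is known and recorded, leaving it out of the treatment comparison has two costs. Outcome variation that it could explain stays in the error term. And if the arms happen to differ in their share of hypertensive women, the estimated CPAP effect moves with that difference and nothing corrects it.

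The logistic model does not clearly fill the gap. It is framed as a search for predictors, its covariates are left open until the data can be seen, and it does not cover DBP, which is the primary outcome.

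A second problem sits underneath. The definitions leave unclear whether a woman with chronic hypertension at entry already counts as having the outcome that Composite 1 measures.

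**Working it through.** **1. The plan's own figures.** Inputs from Protocol section 3.9.1: SD 7.4, difference 2.5 mmHg, two-sided alpha 0.05, power 0.80. Then n per arm = 2 × (1.960 + 0.842)² × 7.4² / 2.5² = 137.5, so 138, or 139 with the t distribution. The plan states 139. For Composite 2, 153 per arm and a control rate of 21.4% (Combined protocol and SAP, secondary outcomes, where the definition still includes gestational diabetes) give power 0.832 for a 12-point fall and 0.970 for a 15-point fall. The plan states 0.83 and 0.97. No stated figure is wrong on this point.

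**2. Precision left unused on a composite.** Let s be the share hypertensive at entry, pa and pb the risks in hypertensive and other women, and p = s·pa + (1−s)·pb. Then R² = s(1−s)(pa−pb)² / [p(1−p)], and the equivalent gain in sample size is 1/(1−R²) − 1. All values of s, pa and pb are assumptions.

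| pa vs pb | s | p | R² | Gain |
|---|---|---|---|---|
| 40% vs 20% | 0.3 | 0.260 | 0.044 | 4.6% |
| 40% vs 20% | 0.5 | 0.300 | 0.048 | 5.0% |
| 45% vs 15% | 0.3 | 0.240 | 0.104 | 11.6% |
| 45% vs 15% | 0.5 | 0.300 | 0.107 | 12.0% |
| 50% vs 15% | 0.3 | 0.255 | 0.135 | 15.7% |
| 50% vs 15% | 0.5 | 0.325 | 0.140 | 16.2% |

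A simulation with a common odds ratio of 0.5 shows what this means for power, comparing chi-square with a logistic model adjusted for entry hypertension. Power went from 0.59 to 0.61 (s = 0.3, 40% vs 15%), from 0.65 to 0.67 (s = 0.5, 40% vs 15%) and from 0.66 to 0.69 (s = 0.3, 50% vs 20%). Outside the range in the table, at s = 0.5 and 60% vs 15%, it went from 0.63 to 0.72.

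**3. Chance imbalance.** With 139 per arm, the 95% range of the between-arm difference in s is ±1.96 × √(2s(1−s)/139). That is ±10.8 points at s = 0.3 and ±11.8 points at s = 0.5. With a 30-point risk gap (45% vs 15%), an imbalance at that limit moves the crude risk difference by 0.30 × 10.8 = 3.2 to 0.30 × 11.8 = 3.5 points.

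**4. DBP.** Adjustment reduces the SD to 7.4 × √(1−R²). For assumed R² of 5%, 10% and 20% this is 7.21, 7.02 and 6.62, and power at 139 per arm rises from 0.80 to 0.82, 0.84 and 0.88. The documents do not say how much of the variation in DBP change entry hypertension explains. A change score has already removed part of any stable difference.

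**5. Definitions side by side.** Protocol section 2.1 lists four categories of hypertensive disorder of pregnancy, and chronic hypertension predating pregnancy is one. The secondary outcomes (Protocol, after section 3.7.2) define Composite 1 as hypertensive disorder of pregnancy, and Composite 2 contains it. Read literally, every criterion (a) woman meets both composites in either arm. The risk in that group would then be 100%, and no CPAP effect on either composite could be estimated in it. The table in step 2 assumes the other reading.

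**6. Effect by entry hypertension.** The interaction SE is 7.4 × √(2/(139s) + 2/(139(1−s))), which is 1.94 at s = 0.3 and 1.78 at s = 0.5. Power for a 2.5 mmHg difference in effect is 0.25 and 0.29.

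**The case against.** The strongest reply is that a randomised comparison is valid without covariates. Chance imbalance is already allowed for in the standard error, and one of five overlapping risk conditions need be neither a stratum nor a model term. The DBP test uses change from baseline, a logistic model for the composites is planned, and every figure for the gain rests on assumed shares and risks. This largely stands. The unadjusted tests are valid, it would be wrong to say that the plan contains no adjustment, and the likely gain in power is modest. What remains is that a recorded baseline variable, probably strongly prognostic, enters no stated estimate of the CPAP effect, and that the planned model does not say what it adjusts for.

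A reader might go further and infer that pooling hides an effect confined to hypertensive women. If 2.5 mmHg applied only to 30%, 40% or 50% of the sample, the pooled effect would be 0.75, 1.0 or 1.25 mmHg, and power at 139 per arm 0.13, 0.20 or 0.29. The arithmetic is right, but the documents do not suggest that scenario. The contrast in section 1.1.3 concerns pre-eclampsia and preterm birth, not blood pressure. The one null blood pressure study it mentions was in gestational hypertension. The contrast is between apparent benefit and no apparent benefit, so the results are not opposite. It comes from 3 small studies, in a review of 7 studies with 111 women in all, that the protocol itself finds inconclusive. Nor would adjustment expose such an effect. In simulation with the effect confined to 30% of women (odds ratio 0.4), crude and adjusted power were 0.26 and 0.26 in one setting and 0.24 and 0.25 in another.

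**Conclusion.** The point holds as a missed gain in precision and a gap in specification. It does not invalidate the planned tests. If 30-50% of women are hypertensive at entry, with risks of 40-50% against 15-20%, adjustment is worth about 5-16% more women on the composites, or roughly 0.02 to 0.03 in power in the simulated settings within that range. A chance imbalance at the 95% limit could shift a crude composite difference by about 3 points. The gain for DBP is probably positive, but its size cannot be fixed from the documents.

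The definitional question comes first. Until it is settled whether chronic hypertension at entry counts as an event, neither the crude nor the adjusted comparison of Composites 1 and 2 has a clear meaning for criterion (a) women.

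The background justifies an exploratory look at the CPAP effect by entry hypertension. It does not support a claim that a null pooled result would be misleading.

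**What to change.** In section 3.10.4, in this order:

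1. Reconcile the definition of hypertensive disorder in section 2.1 with the list of composites, stating whether chronic hypertension present at entry counts as a Composite 1 or Composite 2 event.
2. Add entry hypertension (criterion a or b, yes or no) to the DBP treatment comparison. A yes/no term also settles how to classify women with several risk conditions.
3. Once step 1 is done, compare Composites 1 and 2 by a logistic model with treatment and entry hypertension, reported as a standardised risk difference with its confidence interval. Name this as the treatment comparison, separate from the predictor model.
4. Optionally, report the CPAP effect in women with and without entry hypertension with confidence intervals, labelled exploratory and with no significance claim.

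The cost is SAP wording and one or two model terms on data already collected. The downside lies in step 4: with power of only 0.25 to 0.29 for a 2.5 mmHg difference in effect, the subgroup estimates will be imprecise and open to over-reading. Step 2 or 3 alone will not reveal an effect confined to one group.

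### Nocturnal dipping is named only as a yes/no non-dipping pattern; the continuous night-to-day fall should join the planned mixed model as the main analysis of dipping (minor)

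*Protocol*

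**What the plan says.** The second secondary objective (Protocol, 1.3.2) is "To compare the night-time blood pressure compared to control group". The matching outcome in the secondary outcome list (Protocol, under 3.7.2) is "24-hour ambulatory blood pressure monitoring (daytime versus night time) using the non-invasive technique from pulse transit time". The flow chart schedules this recording at enrolment, 6-8 weeks later in the 2nd trimester, and in the 3rd trimester.

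Section 3.10.4 then has two relevant bullets:

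- Continuous secondary outcomes measured repeatedly, with 24-hour blood pressure monitoring as an example, are compared with baseline in a linear mixed model.
- Categorical secondary outcomes are tested by chi-square or Fisher's exact test. This is the only place in the analysis plan where dipping appears: "individual outcome, control of BP, or non-dipping BP pattern will be compared between CPAP and control groups using" those tests.

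The Combined protocol and SAP has the same two bullets. Neither document names a percentage nocturnal fall or a night/day ratio as an outcome, and neither gives the cut-off that makes a woman a non-dipper. Section 3.5.2 says only that the pattern has been associated with preeclampsia and small for gestational age.

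**The concern.** The fall from day to night is a number that each recording supplies. After a cut, a woman whose fall changes from 2% to 9% and one whose fall does not change count the same if both stay on the same side of the line. A test on the proportion discards that information. The planned chi-square test also uses neither the baseline dip nor the repeated visits, although both are collected.

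The dipping comparison could therefore be reported as showing no difference when there is one, and with no stated cut-off such a result would be hard to interpret.

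**Working it through.** **Inputs from the documents.** "Type I & II error and a ratio of intervention versus control are set at 0.05, 0.2, and 1:1, respectively" (3.9.1). Tests are two-sided (3.10.4). The SD is 7.4 mmHg, for diastolic pressure in a cited study (3.9.1). On the target: "We, therefore, set mean difference of at least 2.5 mmHg, which will require 278 subjects to enroll" (3.9.1), that is, 139 per arm.

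**The plan's own figure.** n per arm = 2 x (1.960 + 0.842)^2 x (7.4/2.5)^2 = 137.5, so 138 against the stated 139. Power at 139 per arm is 0.804 by the normal approximation (0.801 by the t distribution). The plan's figure reproduces. It concerns clinic blood pressure; no power or sample size is stated for any ambulatory outcome.

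**Inputs that had to be assumed.** The SD of the dip, the CPAP effect on it, the cut-off, the share of non-dippers among controls and the number of women with usable recordings are not given. I assume that the dip is normally distributed, that CPAP shifts its mean by d SDs, and that the cut-off leaves a proportion p0 of controls non-dipping. Then:

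- non-dipping proportion on CPAP: p1 = Phi(Phi^-1(p0) - d)
- full-scale power: Phi(d x sqrt(n/2) - 1.960)
- power for the cut: two-proportion test with pooled variance under the null

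**Varying prevalence.** d = 2.5/7.4 = 0.338, borrowed from the primary outcome; 139 per arm; full-scale power 0.804.

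| Controls non-dipping | CPAP non-dipping | Power of the cut | Loss (points) |
|---|---|---|---|
| 10% | 5.3% | 0.317 | 49 |
| 20% | 11.9% | 0.453 | 35 |
| 30% | 19.4% | 0.533 | 27 |
| 40% | 27.7% | 0.581 | 22 |
| 50% | 36.8% | 0.605 | 20 |
| 60% | 46.6% | 0.609 | 20 |
| 70% | 57.4% | 0.590 | 21 |
| 80% | 69.3% | 0.538 | 27 |

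**Varying the effect.** 139 per arm, 50% of controls non-dipping.

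| d | Full scale | Cut | Loss (points) |
|---|---|---|---|
| 0.10 | 0.130 | 0.097 | 3 |
| 0.20 | 0.385 | 0.262 | 12 |
| 0.338 | 0.804 | 0.605 | 20 |
| 0.50 | 0.986 | 0.906 | 8 |
| 0.60 | 0.999 | 0.975 | 2 |

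**Varying the sample size.** With d = 0.338 and 30 to 80% of controls non-dipping, power is 0.84 against 0.57 to 0.65 at 153 per arm (Combined protocol and SAP). At 167 per arm (current Protocol) it is 0.87 against 0.61 to 0.69.

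These are single-visit comparisons. They do not count what a mixed model could add by using baseline and repeated visits.

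**The case against.** A reader might infer that the trial's night-time blood pressure question loses about 20 points of power. The documents do not support that. The objective asks about night-time pressure, not dipping status. Its listed outcome is 24-hour monitoring, daytime versus night time, and 3.10.4 assigns 24-hour monitoring to a linear mixed model. The loss for that question is nil.

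Three further objections have weight.

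- **The effect size is borrowed.** The value 0.338 SD is the plan's target for daytime clinic pressure. If day and night pressure both fell by 2.5 mmHg, the dip would barely move. Take a daytime mean of 92.7 and, for illustration, a 10% dip (a fall of 9.27 mmHg): after treatment it is 9.27/90.2 = 10.3%. A shift in the dip needs an extra night-time fall, which the documents nowhere quantify. This stands, so no single figure for the loss can be attributed to the plan.
- **Both bullets are open lists.** The mixed model could therefore carry the day-night contrast. That is possible, but the text does not say which summary of the recording is modelled, and dipping itself is named only as a category. Night-time level and day-to-night fall are also different quantities, as the example shows, so a model of level does not stand in for an analysis of the dip.
- **The categorical pattern has a clinical rationale** in 3.5.2, and dropping a prespecified comparison is not needed to gain the better test. This stands: the proportion can stay.

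**Conclusion.** The point holds for the dipping comparison only. As a named outcome, dipping is tested solely as a yes/no pattern with no stated cut-off, although its continuous form can be derived from recordings already scheduled.

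The size rests on assumptions: a normally distributed dip, an effect taken from another outcome, and an assumed prevalence. At 0.338 SD and 139 per arm, 0.80 on the full scale compares with about 0.53 to 0.61 for the cut over 30 to 80% non-dipping. Over all the settings tabulated, the loss runs from about 2 points to a little under 50. About 20 points is what this model gives for a cut near the middle of the distribution when the full-scale test has 80% power; it is not a figure that the documents supply.

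Severity is low: this is a secondary comparison with no power claim, beside a continuous ambulatory blood pressure analysis.

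**What to change.** In 3.10.4:

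- Add the percentage nocturnal fall, 100 x (daytime mean - night-time mean)/daytime mean, for systolic and diastolic pressure, to the continuous outcomes in the linear mixed model already planned for 24-hour monitoring. Include the baseline value and make this the main analysis of dipping.
- Keep the non-dipping proportion per arm as a supporting comparison with its confidence interval, and state the cut-off that defines it.

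The cost is some SAP wording and one more derived secondary variable, with no new visits or data. The small downside is that a mean difference in percentage fall is less familiar to clinicians than a proportion of non-dippers, which remains in the report.
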